12.6.3.2 Human Smoking Topography Parameters

The HST assessments will take place on Day 0, Day 1 and Day 4 in the THS 2.2 and CC arms only, if CC are compatible with the HST SODIM[®] device.

The per puff parameters are shown in **Table 8** and the per cigarette parameters are shown in **Table 9**.

The per-cigarette parameters derived from the HST assessments will be summarized along with their changes from baseline. The per-puff and per-cigarette parameters will be listed. In addition the product mean and 95% CI per cigarette parameters will be presented graphically.

The per-cigarette parameters will be analyzed on Days 1 and 4 separately using an ANCOVA model on the log-transformed HST parameter with terms for log-transformed baseline score, sex, average daily CC consumption over the last 4 weeks as reported during screening, product. No adjustment will be made for multiple comparisons.

The SAS code will be the same as described in Section **12.6.1.1 “Primary Biomarkers of Exposure in 24 hour collection”**.

LS means for each product along with the ratio (THS 2.2 : CC) and 95% CI will be presented in the tables.

All figures, summaries and analyses will be performed on the FAS.

The data will be presented in the below outputs, the TFL number refers to the TFL number in the accompanying TFL shell document:

TFL number	Title
FIGURES	
15.1.2.39	HST per Cigarette Parameters Arithmetic Mean and 95% CI– FAS
TABLES	
15.2.4.63	Descriptive Statistics of HST Parameters per Cigarette – FAS
15.2.4.64	Analysis of HST per Cigarette – FAS
LISTINGS	
15.3.7.1	Listing of HST Assessments

12.6.3.3 Human Smoking Topography Questionnaire

The HST questionnaire will be administered on Days 0 and 4.

The number and percentage of subjects in each category of the items of the questionnaire will be summarized. The individual responses will be listed.

All summaries will be performed on the FAS.

The data will be presented in the below outputs, the TFL number refers to the TFL number in the accompanying TFL shell document:

TFL number	Title
TABLES	
15.2.4.65	Descriptive Statistics of HST Questionnaire Data – FAS
LISTINGS	
15.3.7.2	Listing of HST Questionnaire Results

12.6.3.4 CYP2A6 Activity

CYP2A6 activity will be measured in plasma on Days 0 and 6. In this study the CYP2A6 activity will be calculated using the metabolic ratio of trans 3' hydroxycotinine and cotinine, as described in Section 7.1.5 "CYP2A6". Descriptive statistics of the values and change on Day 6 from Day 0 and supportive listings will be provided.

The analysis will compare the Day 6 values (both absolute and change from baseline) between the THS 2.2 and CC arms between the THS 2.2 and SA arms. An ANCOVA model will be used with terms for baseline, sex, average daily CC consumption over the last 4 weeks as reported during screening and product. No adjustment will be made for multiple comparisons.

The SAS code will be the same as described in Section 12.6.1.1 "Primary Biomarkers of Exposure in 24 hour collection".

LS means for each product along with the difference (THS 2.2 - CC) and 95% CI will be presented in the tables

CYP2A6 activity will also be examined to compare the reductions in THS 2.2 vs. SA using the same methodology as above.

The data will be presented in the below outputs, the TFL number refers to the TFL number in the accompanying TFL shell document:

TFL number	Title
TABLES	
15.2.4.56	Descriptive Statistics of CYP2A6 Activity (%) – FAS
15.2.4.57	Analysis of CYP2A6 Activity – FAS
LISTINGS	
15.3.6.15	Listing of CYP2A6 Activity and Changes from Baseline

12.6.3.5 Relationship between BoExp and NEQ

The analysis of the relationship between NEQ and primary and secondary BoExp will be reported in a separate report as stated in Section 9 "CHANGES FROM THE PROTOCOL SPECIFIED STATISTICAL ANALYSIS".

12.6.3.6 Risk Markers

The risk markers are 8-epi-PGF2 α and 11-DTX-B2 in urine and will be presented as quantity excreted over 24 hours and concentration adjusted for creatinine.

The quantity excreted over 24 hour, percent changes in the quantity excreted and the concentration adjusted for creatinine in 24 hour urine will be listed and summarized. In addition line graphs will be produced for product means (and 95% CI) over all timepoints.

The analysis will compare the concentrations adjusted for creatinine and the quantity excreted over 24 hour on Day 5 between the THS 2.2 and CC arms, and between the THS 2.2 and SA arms. An ANCOVA model will be used with terms for Day 0 concentration adjusted for creatinine or quantity excreted over 24 hours, sex, average daily CC consumption over the last 4 weeks as reported during screening and product. No adjustment will be made for multiple comparisons.

If there is evidence of non-normality (see Section 12.6, “Planned Statistical Analyses” then the concentrations or quantity excreted will be transformed prior to analysis.

The SAS code will be the same as described in Section 12.6.1.1 “Primary Biomarkers of Exposure in 24 hour collection”.

LS means for each product along with the difference (THS 2.2 - CC) and 95% CI will be presented in the tables.

The data will be presented in the below outputs, the TFL number refers to the TFL number in the accompanying TFL shell document:

TFL number	Title
TABLES	
15.2.4.58	Analysis of Urinary 8-epi-PGF2 α on Day 5 – FAS
15.2.4.59	Descriptive Statistics of Urinary 8-epi-PGF2 α – FAS
15.2.4.60	Analysis of Urinary 11-DTX-B2 on Day 5 – FAS
15.2.4.61	Descriptive Statistics of Urinary 11-DTX-B2 – FAS
LISTINGS	
15.3.3.3	Listing of Risk Markers and Collection Times

12.6.3.6.1 Relationship Between Risk Markers, BoExp and NEQ

The relationship between risk markers and BoExp will not be reported as stated in Section 9 “CHANGES FROM THE PROTOCOL SPECIFIED STATISTICAL ANALYSIS”.

The relationship between risk markers, and NEQ will be examined by fitting a general linear model (glm) with terms for baseline and Day 5 NEQ for each treatment arm separately. The SAS code to be used is as shown below:

```
Proc glm data=_data_ ;
Model Risk marker = baseline NEQ Day 5 NEQ;
Run;
```

The slope along with 95% CIs and the p-value will be presented for each analysis.

In addition scatterplots of each risk marker separately with NEQ, with the regression from the above model shown on the plot if there was a significant slope from the above model.

In these plots the risk marker will be on the y-axis.

The data will be presented in the below outputs, the TFL number refers to the TFL number in the accompanying TFL shell document:

TFL number	Title
FIGURES	
15.1.2.40	Scatterplot of 8-epi-PGF2 α Urinary Concentration Adjusted for Creatinine vs. NEQ Urinary Concentration Adjusted for Creatinine – FAS
15.1.2.41	Scatterplot of Urinary 8-epi-PGF2 α Quantity Excreted over 24 hours vs. Urinary NEQ Quantity Excreted over 24 hours – FAS
15.1.2.42	Scatterplot of 11-DTX-B2 Urinary Concentration Adjusted for Creatinine vs. NEQ Urinary Concentration Adjusted for Creatinine – FAS
15.1.2.43	Scatterplot of Urinary 11-DTX-B2 Quantity Excreted over 24 hours vs. Urinary NEQ Quantity Excreted over 24 hours– FAS
TABLES	
15.2.4.62	Statistical Analysis of the Relationship Between Risk Markers and NEQ – FAS

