7.1.2 Risk Markers

For those risk markers measured in urine an adjustment of the concentration for creatinine in urine will be calculated as:

$$\text{Risk Marker (corrected for creatinine)} = \frac{[\text{Risk Marker}]}{[\text{Creatinine}]}$$

where the concentrations are measured from the same 24 hour urine collection.

The quantity excreted for the risk markers measured in urine over 24 hours will be calculated as:

$$\text{Quantity Excreted over 24 hours} = [\text{Risk Marker}] * \text{urine volume}$$

where the concentration and the urine volume are from the same 24 hour urine collection.

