7.1.3 Nicotine Equivalents

The quantity excreted of NEQ over 24 hours will be derived according to the formula below. The concentrations reported for free nicotine and its five major metabolites will not be used as analysis variables.

$$\begin{aligned} \text{NEQ [g]} &= (\text{free nicotine}_c [\mu\text{mol/L}] + \text{nicotine-glucuronide}_c [\mu\text{mol/L}] \\ &+ \text{free cotinine}_c [\mu\text{mol/L}] + \text{cotinine-glucuronide}_c [\mu\text{mol/L}] \\ &+ \text{free } \textit{trans}\text{-3'-hydroxycotinine}_c [\mu\text{mol/L}] \\ &+ \textit{trans}\text{-3'-ydroxycotinine-glucuronide}_c [\mu\text{mol/L}]) \\ &* 162.2 [\mu\text{g}/\mu\text{mol}] * \text{urine volume (L)} / 1000 [\mu\text{g}/\text{mg}] \end{aligned}$$

N.B. All concentrations must be in $\mu\text{mol/L}$ before applying the above formula.

The conversion factors will be applied as follows:

Free nicotine	The molecular weight is 162.232 g/mol (Chemical Information Specialized Information Services RN:54-11-5). Therefore to convert nicotine from ng/mL to ng/mol, the result in ng/mL is multiplied by 6.164.
Nicotine glucuronide	The molecular weight is 338.356 g/mol (Chemical Information Specialized Information Services RN:152306-59-7). Therefore to convert nicotine from ng/mL to ng/mol, the result in ng/mL is multiplied by 2.955.
Cotinine	The molecular weight is 176.218 g/mol (Chemical Information Specialized Information Services RN:486-56-6). Therefore to transform cotinine from ng/mL to nmol/L, the result in ng/mL will be multiplied by 5.675.
Cotinine-glucuronide	The molecular weight is 352.341 g/mol (Chemical Information Specialized Information Services RN:139427-57-9). Therefore to transform cotinine from ng/mL to nmol/L, the result in ng/mL will be multiplied by 2.838.
Trans-3'hydroxycotinine	The molecular weight is 192.217 g/mol (Chemical Information Specialized Information Services RN:34834-67-8). Therefore to transform trans-3' hydroxycotinine from ng/mL to nmol/L, the result in ng/mL is multiplied by 5.202.
Trans-3'hydroxycotinine-glucuronide	The molecular weight is 368.34 g/mol (Chemical Information Specialized Information Services RN:132929-88-5). Therefore to transform trans-3' hydroxycotinine from ng/mL to nmol/L, the result in ng/mL is multiplied by 2.715.

The adjustment of NEQ for creatinine in urine will be calculated as:

$$\text{NEQ (corrected for creatinine)} = \frac{[\text{NEQ}]}{[\text{Creatinine}]}$$

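### The creatinine-adjusted regression of risk marker on NEQ divides both Day 5 variables by the same creatinine and has no creatinine term, so it can show a positive slope when the two are unrelated

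*SAP*

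**What the plan says.** For marker against NEQ, the analysis text of SAP 12.6.3.6.1 reads: "will be examined by fitting a general linear model (glm) with terms for baseline and Day 5 NEQ for each treatment arm separately". In code this becomes "Model Risk marker = baseline NEQ Day 5 NEQ". There is no term for creatinine, urine volume, sex or cigarette consumption, and no log transformation is specified. Each fit reports a slope, a 95% CI and a p-value (Table 15.2.4.62), and a regression line goes on the scatterplot only if the slope is significant.

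The figures show which expressions are meant. Figures 15.1.2.40 and 15.1.2.42 have both axes adjusted for creatinine: "Scatterplot of 11-DTX-B2 Urinary Concentration Adjusted for Creatinine vs. NEQ Urinary Concentration Adjusted for Creatinine" (and likewise for 8-epi-PGF2α). Figures 15.1.2.41 and 15.1.2.43 have both axes as amounts: "Scatterplot of Urinary 11-DTX-B2 Quantity Excreted over 24 hours vs. Urinary NEQ Quantity Excreted over 24 hours".

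On derivation, SAP 7.1.2 divides the marker concentration by the creatinine concentration, "where the concentrations are measured from the same 24 hour urine collection". SAP 7.1.3 divides NEQ by creatinine too ("The adjustment of NEQ for creatinine in urine will be calculated as"). Protocol 7.7.2 and Table A2 show that NEQ, markers and creatinine all come from the one collection that starts on Day 5.

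**The concern.** When two unrelated quantities are divided by a common third quantity, the ratios become positively correlated. Here the divisor on both sides is Day 5 creatinine, and nothing in the model accounts for it. The baseline NEQ term absorbs part of the effect when a subject's creatinine is stable from day to day, but not all of it.

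SAP Section 9 drops the marker-versus-BoExp analysis and moves NEQ-versus-BoExp to a separate report, so marker versus NEQ is the only relationship analysis left for the clinical study report. An artefact would always point the same way, with the marker appearing to rise with nicotine uptake. Because the line is drawn only for significant slopes, the figure would display it as a finding.

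**Working it through.** **No planned figure to reproduce.** The SAP gives no power or error rate for this regression. The check is what its model does when marker and NEQ are generated independently.

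**Inputs from the documents.** Arms of 80, 40 and 40. For 11-DTX-B2, SAP Section 8 states that 24.71 ng/g creatinine is a 20% difference, with an SD of 43.78:

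- mean = 24.71 / 0.20 = 123.55
- CV = 43.78 / 123.55 = 0.354
- log SD of the ratio = √ln(1 + 0.354²) = 0.344

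**Inputs assumed, because the documents give none.** Log SD of 24-hour creatinine 0.10-0.30; log SD of NEQ excretion 0.4-0.6, central value 0.5; Day 0/Day 5 correlation 0.6 for NEQ and 0.85 for creatinine. The marker in the model is taken to be the Day 5 value, which the SAS statement does not say.

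**Mechanism.** In one collection, a ratio of concentrations equals the ratio of 24-hour amounts. Write m, n and c for the logs of the marker, NEQ and creatinine amounts. The model then relates m − c to n − c. If m, n and c are independent,

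corr(m − c, n − c) = s_c² / [SD(m − c) × √(s_n² + s_c²)].

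With SD(m − c) = 0.344 and s_n = 0.5:

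- s_c = 0.10: 0.01 / (0.344 × 0.510) = 0.06
- s_c = 0.20: 0.04 / (0.344 × 0.539) = 0.22
- s_c = 0.30: 0.09 / (0.344 × 0.583) = 0.45

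**Simulated two-sided 5% rejection of the Day 5 NEQ slope.** This is the SAP's two-term model on the raw ratios, with excretions unrelated to creatinine, the ratio's log SD held at 0.344 and NEQ log SD 0.4-0.6:

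| Creatinine log SD | n=80 | n=40 |
|---|---|---|
| 0.10 | 6-7% | 6% |
| 0.15 | 9-13% | 7-9% |
| 0.20 | 16-28% | 11-18% |
| 0.25 | 31-53% | 19-32% |
| 0.30 | 52-82% | 31-53% |

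At the central NEQ log SD of 0.5, the range over the whole column is about 6-69% at n=80 and 6-39% at n=40.

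**If excretion scales with creatinine.** With both excretions scaling partly, rejection is about 5-11%. If the marker scales fully, m − c no longer contains c, and rejection is 4.6-5.5%.

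**Quantity-excreted fit.** Concentration times volume is the amount excreted, so dilution cancels and no divisor is shared. With complete collection, and excretions that do not scale with creatinine, rejection is 5.0% (n=80) and 5.2% (n=40). The ±20 minute window at each end is 20/1440 = 1.4% to 40/1440 = 2.8% of the collection; errors of that size give 4.9-5.5%. A 10% collection error gives 10% and 7%; a 20% error gives 47% and 27%. If both excretions rise with creatinine (body size), each amount contains + c instead of − c. The common term returns with its sign reversed on both sides, and the slope is again pushed upward.

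**Candidate corrections on the creatinine scale.**

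- Log scale with log creatinine added: 4-6% in every scenario.
- Log scale alone: still 35% significant positive slopes in one setting (n=80, creatinine CV 0.3, NEQ CV 0.5).
- Raw scale with an untransformed creatinine term: 6-7% at creatinine CV 0.2, 8-18% at 0.3, 12-49% at 0.4.
- Sex term alone (n=80, assumed male/female creatinine ratio 1.4, within-sex CV 0.2): significant positive slopes fall only from 26% to 18%, against a nominal 2.5%.

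**The case against.** The strongest reply is that the large rates belong to the least favourable null. Creatinine spread, NEQ spread and the day-to-day correlations are all assumed. So is the absence of any link between excretion and creatinine, and under that assumption adjusting for creatinine would serve no purpose. The rates also depend on how the marker's spread is set. If 0.344 is taken as the log SD of excretion and not of the ratio, they are 10% (n=80) and 7% (n=40) at creatinine log SD 0.15, and 27% and 15% at 0.25. This stands: the size ranges from nothing to large, and the documents cannot settle it.

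The plan also has a partial internal check. A slope caused only by the divisor would appear on the creatinine scale and not on the quantity scale. That stands too, although the SAP does not say the two will be read together, and body size can confound the quantity fit.

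Three stronger readings are tempting and not supported:

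- **Urine volume as a shared nuisance factor.** A reader might infer that it acts as creatinine does. SAP 7.1.2 takes volume and concentration from one collection ("where the concentration and the urine volume are from the same 24 hour urine collection"), so their product is the amount excreted. Protocol 7.7.2 requires all urine to be collected in confinement with times recorded, and SAP Table 14 makes start or end times outside 30 minutes a major deviation.
- **Omission of sex as an inconsistency.** The risk-marker comparison in SAP 12.6.3.6 does adjust for sex ("An ANCOVA model will be used with terms for Day 0 concentration adjusted for creatinine or quantity excreted over 24 hours, sex"), but that is a between-arm model and this is a within-arm regression. Sex alone would not cure the problem in any case.
- **Near-certain false positives in the abstinence arm through LLOQ/2 imputation.** That needs nearly all Day 5 NEQ values in that arm to be below quantification. The documents give neither the limits nor the expected levels.

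**Conclusion.** The point holds for the creatinine-adjusted fits: two markers in three arms, 2 × 3 = 6 of the 12 planned regressions. Both Day 5 variables carry the same divisor, no model term deals with it, and nothing elsewhere in the protocol or SAP supplies one. The inflation is conditional: slight at a creatinine log SD of 0.10, serious from about 0.20 if excretions are unrelated to creatinine, small if both scale partly with it, and absent if the marker scales fully. The 6-69% and 6-39% ranges describe what the model permits and are not an estimate of this trial's error rate.

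The analysis is exploratory. No primary or secondary result and no success criterion depends on it. The change is still worth making, because the adjusted model held 4-6% in every scenario using data already collected.

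**What to change.** In SAP 12.6.3.6.1, for each marker and arm, regress log Day 5 marker on log baseline NEQ and log Day 5 NEQ, and add log 24-hour creatinine excretion (concentration × volume) on Day 5 and Day 0. Sex is an optional extra. Report this adjusted NEQ slope in Table 15.2.4.62. Keep the ratio scatterplots as descriptive, with no regression line from the unadjusted ratio fit.

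Cost: SAP wording and a few degrees of freedom. With both creatinine terms and sex, residual degrees of freedom go from 40 − 3 = 37 to 40 − 6 = 34, or from 80 − 3 = 77 to 80 − 6 = 74.

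One consequence should be stated. With both days' creatinine in the model, the two expressions give the same NEQ slope. From m − c5 = α + β0(n0 − c0) + β5(n5 − c5) + γ5·c5 + γ0·c0 it follows that m = α + β0·n0 + β5·n5 + (1 − β5 + γ5)c5 + (γ0 − β0)c0, with β5 unchanged. The 12 fits reduce to 6, and the quantity scale is no longer a separate check.

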12.6.3.7 Ames Mutagenicity Test

The 24 hour urine collection for the Ames mutagenicity test will be performed on Day 0 and Day 5.

Descriptive statistics of the values and change on Day 5 from Day 0 of the YG1024+S9 mutagenicity will be provided, along with listings.

The data will be presented in the below outputs, the TFL number refers to the TFL number in the accompanying TFL shell document:

TFL number	Title
TABLES	
15.2.4.47	Descriptive Statistics of Ames Mutagenicity Test (YG1024+S9) (units) – FAS
LISTINGS	
15.3.5.1	Listing of Mutagenicity Results and Changes from Baseline

12.6.3.8 Visual Inspection of the Tobacco Plugs

The collection of the tobacco plugs from the THS 2.2 products will be performed on Days 1 to 5. The number and percentage of tobacco plugs showing each of the following criteria will be summarized by day: Ashes not anymore visible when shooting picture; No tobacco in plug; Not enough tobacco in the plug to perform the analysis; Tobacco plug destroyed, analysis impossible; No tobacco plug in the vial; Other error.

The data will be presented in the below outputs, the TFL number refers to the TFL number in the accompanying TFL shell document:

TFL number	Title
TABLES	
15.2.4.66	Descriptive Statistics of Visual Inspection of the THS 2.2 Tobacco Plugs Data – FAS
LISTINGS	
15.3.6.16	Listing of Visual Inspection of the Tobacco Plugs Results

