7.8.2 Visual Inspection of Tobacco Plugs

All tobacco plugs collected during the study will be sent to the Sponsor for subsequent visual inspection to determine whether combustion occurred during product use.

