5.3 Exploratory Objectives and Endpoints

1. To describe the following parameters in smokers switching from CC to THS 2.2 as compared to smokers continuing to smoke CC and smokers switching from CC to SA:

Endpoints:

- Ames Mutagenicity test (YG1024+S9).
- Questionnaire of Smoking Urges (brief version) [QSU-brief] total score, factor 1 (relief) and factor 2 (reward) (Cox et al. 2001).
- Minnesota Nicotine Withdrawal Scale (MNWS) total score (Hughes and Hatsukami 2008).

- CYP2A6 enzymatic activity as molar ratio of 3-hydroxycotinine and cotinine
 - Selected risk markers (expressed as quantity excreted and concentration adjusted for creatinine) in 24-hour urine:
 - 8-epi-prostaglandine F2 α (8-epi-PGF2 α)
 - 11-dehydro-thromboxane B2 (11-DTX-B2)
2. To evaluate in smokers switching from CC to THS 2.2, smokers continuing smoking CC and smokers switching from CC to SA the relationship between¹:

Endpoints:

- Primary and secondary BoExp and NEQ:
- NEQ in urine by:

– Blood COHb.	– Exhaled CO
and urinary BoExp (expressed as quantity excreted and concentration adjusted for creatinine) in 24-hour urine	
– MHBMA.	– o-tol.
– 3-HPMA.	– CEMA.
– S-PMA.	– HEMA.
– 1-OHP.	– B[a]P.
– Total NNN.	– HMPMA.
– 4-ABP.	– S-BMA.
– 1-NA.	– Total NNAL.
– 2-NA.	

¹ The reporting of this objective will be the subject of a separate report.

- Selected risk markers and NEQ² :
 - NEQ in urine by:
and urinary risk markers (expressed as quantity excreted and concentration adjusted for creatinine) in 24-hour urine
 - 8-epi-PGF2 α .
 - 11-DTX-B2.
3. To describe the following parameters over the course of the study in smokers switching from CC to THS 2.2 as compared to smokers continuing smoking CC:
- Endpoints:
- The subscales from the Modified Cigarette Evaluation Questionnaire (MCEQ) (Cappelleri et al. 2007).
 - The following parameters measured per cigarette from the human smoking topography (HST) device.
 - Total number of puffs.
 - Total puff volume.
 - Average puff volume.
 - Average puff duration.
 - Total puff duration.
 - Average flow.
 - Average Peak flow.
 - Total inter puff interval.
 - Average inter puff interval.
 - Total smoking duration.
 - Total work.
 - Average work.
 - Average pressure drop.
 - Average peak pressure drop.
 - Smoking intensity.
 - Puffing time index.
 - Puff frequency.
 - HST questionnaire.
4. To describe the following parameter over the course of the study in smokers switching from CC to THS 2.2:
- Endpoints:

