- Potential combustion occurrences in tobacco plugs: visual inspection of the tobacco plugs.

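### SAP 12.6.3.8 names no combustion outcome among the tobacco-plug categories to be counted, so the summary as described gives no combustion frequency

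*SAP*

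**What the plan says.** The fourth exploratory objective in SAP 5.3 reads "To describe the following parameter over the course of the study in smokers switching from CC to THS 2.2", and its endpoint is "Potential combustion occurrences in tobacco plugs: visual inspection of the tobacco plugs". Protocol 3.4.3 gives the same endpoint. Under Protocol 6.5.2, the plugs of all used Tobacco Sticks are separated and kept from Day 1 to Day 5. Protocol 7.8.2 has them sent to the sponsor for "visual inspection to determine whether combustion occurred during product use".

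SAP 12.6.3.8 is the only section that defines the summary: "The number and percentage of tobacco plugs showing each of the following criteria will be summarized by day". The criteria are "Ashes not anymore visible when shooting picture; No tobacco in plug; Not enough tobacco in the plug to perform the analysis", followed by "Tobacco plug destroyed, analysis impossible; No tobacco plug in the vial; Other error". The planned outputs are Table 15.2.4.66, a descriptive table of the inspection data, and Listing 15.3.6.16, titled "Listing of Visual Inspection of the Tobacco Plugs Results".

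Two general provisions bear on this. SAP 12.1 restricts summary statistics to data for which the SAP gives detail. SAP Section 3 places the detailed layout of tables and listings in a separate shell document.

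**The concern.** The inspection asks a yes/no question of each plug: did it burn? The list of things to be counted contains neither answer. It gives reasons why an answer might be missing, plus one code about ashes whose meaning is unclear. A programmer working from the SAP text alone would produce a table showing how often inspection went wrong, with no row for plugs inspected successfully and no result for them.

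At stake is the only frequency summary planned for this endpoint. The categories would also have to be settled later, possibly once inspection results are known, whereas fixing them in the SAP takes a sentence or two.

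**Working it through.** The plan states no figure to reproduce, so the check is a comparison of texts.

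**1. Each criterion in SAP 12.6.3.8 against the endpoint**

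| Criterion (paraphrased) | What it records | States combustion yes or no? |
|---|---|---|
| Ashes no longer visible at the photograph | Ambiguous: the wording suggests ashes were seen earlier, but what it records is their absence from the picture | No |
| Plug contains no tobacco | Failure | No |
| Too little tobacco to analyse | Failure | No |
| Plug destroyed | Failure | No |
| Vial contains no plug | Failure | No |
| Any other error | Error | No |

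Six criteria: five are failure or error codes, one is ambiguous, and none is an outcome. The list closes with a residual error category, which suggests that the items before it are errors too, but the SAP does not say so.

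**2. Whether an outcome is defined elsewhere.** SAP Table 10 (categorical variables) has no combustion variable. SAP Section 9 (changes from the protocol) narrows another exploratory objective, on relationships between markers and nicotine equivalents, but leaves this one alone. The endpoint is therefore still live.

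**3. What the described table can tell a reader.** Let *f* be the share of plugs given one of the six codes on a day, assuming one code per plug. The other 1 − *f* were inspected, and the table does not split them by result.

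- If none of the six codes denotes combustion, the table is compatible with any share of recorded combustion from 0 to 1 − *f*.
- If the ashes code, with share *a*, does denote combustion, the range is *a* to *a* + (1 − *f*).

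Under either reading the frequency is not determined. The ashes code supplies at most a lower limit.

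**4. Denominator.** None is stated. The percentages are described as percentages of plugs, yet one code applies to a vial holding no plug. The base therefore cannot simply be plugs present. Sticks used, vials received and plugs assessable would give different percentages.

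**The case against.** The strongest reply is that the SAP prose is not the table. The shell is a separate document, the title of Table 15.2.4.66 is broad enough to cover results, and the six items may be only the error codes beneath result rows that the shell contains. This cannot be excluded, and it limits the point to what the SAP describes. It does not remove the point. SAP 12.1 ties summaries to what the SAP details, and the only shell changes that SAP Section 3 exempts from amendment concern numbering and titles.

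Second, Protocol 12.6.3 says exploratory endpoints will in general be summarized as in Protocol 12.1.3, which provides frequencies for categorical data. That leaves room for a combustion row, and it means the text should not be read as a decision to withhold one. It does not define the categories, and the SAP's own list is the more specific instruction.

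Third, the listing is of inspection results, and SAP 12.1 calls for listings of all data the protocol requires. If the plug-level result is in the database, it should be listed and a reader could count it. This stands: a reader might infer that combustion will go unreported altogether, and the documents do not support that. A listing is still not the frequency summary, and its contents are not described.

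Fourth, a reader might infer that all six criteria are inspection failures. The ashes item does not allow that to be said flatly.

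Fifth, on the denominator, plugs collected that day is a natural reading. The request is only that it be written down. A count of subjects with at least one combusted plug is a preference that nothing in the documents requires.

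**Conclusion.** The point holds in limited form. The criteria listed in SAP 12.6.3.8 include no combustion result, so the summary as described produces no combustion frequency, by day or overall, for an endpoint that both documents retain. This is a wrong category list in the SAP text rather than a missing refinement.

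The reach is small: one descriptive table for one exploratory objective in the planned 80-subject THS 2.2 arm. A reader might infer that the exposure-reduction conclusion is weakened, because the product is presented as heating rather than burning tobacco. The documents do not support that. Success under SAP 5.5.2 rests on four biomarkers measured on Day 5, whatever the plugs show. The primary analysis, sample size, type I error and analysis populations are unaffected.

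The conclusion assumes that the SAP text governs what is summarized, as SAP 12.1 says. If the shell already carries result rows, what remains is to bring the SAP text into line with it.

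**What to change.** Amend SAP 12.6.3.8 before database lock so that Table 15.2.4.66 reports, by day:

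- the number and percentage of plugs with combustion observed, combustion not observed, and not assessable, with the existing codes kept as reasons for not assessable;
- how the ashes code maps to these three outcomes;
- the denominators: plugs collected, for the assessable/not assessable split, and plugs assessable, for the combustion percentages.

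State that Listing 15.3.6.16 shows the plug-level outcome, and align the shell. A count of subjects with at least one combusted plug is optional.

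The cost is a few table rows and a short definition, because collection and inspection are already planned. One item needs confirming: neither document shows how the inspection result is coded. If only error codes are transferred to the database, the result field has to be added to the transfer as well.
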